A total of 420 adult subjects were randomized to active and vehicle in a 2:2:2:1:1 fashion. Study treatments continued for 12 weeks. Subjects returned to the study clinic at Weeks 1, 2 (phone call only), 4, 8 and 12 (study exit).

The results of the study showed that all three Olumacostat Glasaretil Gel treatment groups demonstrated statistically significantly greater reductions in the absolute change in inflammatory lesion counts from baseline to Week 12 than the combined vehicle group. The LS mean changes in inflammatory lesion counts were -14.6 and -14.5, and -15.0 for the Olumacostat Glasaretil Gel, 4.0% QD, 7.5% QD, and 7.5% BID groups, respectively, compared with -10.7 for the combined vehicle QD group (P = 0.011, P = 0.014, and P = 0.011 respectively). All 3 Olumacostat Glasaretil Gel treatment groups showed statistically significantly greater reductions in the absolute change in noninflammatory lesion counts from baseline to Week 12 than the combined vehicle group. The LS mean changes in noninflammatory lesion counts at Week 12 were -15.3, -13.4, and -17.5 for the DRM01B Olumacostat Glasaretil Gel 4.0% QD, 7.5% QD, and 7.5% BID groups, respectively, compared with -9.3 for the combined vehicle group (P = 0.004, P = 0.050, and P < 0.011 respectively).

The Olumacostat Glasaretil Gel 4.0% QD and 7.5% BID groups each had a statistically significantly greater proportion of subjects achieve a minimum 2-grade improvement (reduction) in IGA score from baseline at Week 12 compared with the combined vehicle group. The percent of subjects achieving this endpoint was 21.6% in the Olumacostat Glasaretil Gel 4.0% QD and 25.9% of subjects in the Olumacostat Glasaretil Gel 7.5% BID group (compared with 9.8% in the combined vehicle QD group (P = 0.024 and P = 0.004, respectively).

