4.1.2 Method of Assigning Subjects to Treatment Groups

A randomization schedule will be generated by a member of the Statistical Services department at QST Consultations, Ltd. (QST) who is not associated with the conduct or analysis of the study, using a validated system. The randomization list will not be stratified but stratification by site will be completed within the Interactive Web-based Randomization System (IWRS).

At the Baseline/Day 1 visit, qualified subjects will be randomized to treatment using the IWRS. The IWRS will assign a study drug kit number based on the subject's treatment assignment and available inventory at the investigational site. The kit number will be recorded in the electronic case report form. Approximately 467 subjects will be randomized to active treatment and approximately 233 subjects will be randomized to vehicle treatment for a total of approximately 700 subjects. Subjects will be randomized to treatment groups in such a manner to balance treatment allocation within study sites in a 2:1 fashion.

Statistical Analysis Plan for Dermira, Inc. Protocol Number: DRM01B-ACN03

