4.2 Determination of Sample Size

The sample size for this study was based on estimates from the DRM01B-ACN02 study observed Week 12 results. Estimates were combined for all three active treatment groups as well as for the two vehicle groups. All power calculations were performed with nQuery Advisor Version 7.0 for a two-sided test at alpha = 0.05.

For inflammatory lesion change a sample size of 300 Olumacostat Glasaretil Gel and 150 Olumacostat Glasaretil Gel, Vehicle subjects has at least 95% power to detect a statistically significant difference with a significance level of 0.05 using the estimated absolute change from Baseline in treatment means of -15.21 and -9.7 for Olumacostat Glasaretil Gel versus its vehicle, respectively, with a standard deviation (SD) of 11.00.

For non-inflammatory lesion change a sample size of 450 Olumacostat Glasaretil Gel and 225 Olumacostat Glasaretil Gel, Vehicle subjects has 95% power to detect a statistically significant difference with a significance level of 0.05 using the estimated absolute change from Baseline in treatment means of -14.73 and -9.70 for Olumacostat Glasaretil Gel versus its vehicle, respectively, with a SD of 16.72.

The success rate for dichotomized IGA is estimated to be 20.5% in the Olumacostat Glasaretil Gel subjects and 9.6% in vehicle subjects. A sample size of 444 Olumacostat Glasaretil Gel and 222 Olumacostat Glasaretil Gel, Vehicle will have 95% power to detect a statistically significant difference in proportions of successes. These calculations were performed with nQuery Advisor Version 7.0 for a two-sided continuity corrected chi-square test at alpha = 0.05.

To allow for a slight loss in power due to dropouts and withdrawals as well as to accommodate sufficient power in all three co-primary variables, a sample of 700 subjects randomized to 2 to 1 for Olumacostat Glasaretil Gel (n=467) and vehicle (n=233), respectively, will be enrolled in the trial.

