7.9.7.1 Primary Efficacy Analyses

Absolute change from Baseline to Week 12 in inflammatory and non-inflammatory lesion counts will be analyzed using either parametric or non-parametric methods consistent with the statistical assumptions required to support the analyses. Specifically, the tests of superiority will be based on an ANCOVA with factors of treatment group and analysis center and the respective baseline lesion count as a covariate or on ranked data submitted to an ANCOVA with factors of treatment group and analysis center and the respective baseline lesion count as a covariate. If the treatment group by analysis center interaction effect is significant at an alpha less than 0.10, then the effect will be included in the model; otherwise it will be omitted.

A skewness test, based on the methods presented by J.H. Zar (1984) [1], will be applied to the residuals resulting from an ANCOVA. A two-sided p-value for the skewness test significant at 0.01 will imply the use of the non-parametric method. If a parametric analysis is indicated, the results of the parametric analysis will be considered the primary analysis. Should a non-parametric analysis be indicated, the absolute or percent changes in inflammatory and non-inflammatory lesions will be rank-transformed prior to submitting them to the ANCOVA. Results of the rank-transformed analyses then will be considered the primary analysis; however, results of the non-ranked transformed analyses will also be presented. That is, the primary

analyses for inflammatory and non-inflammatory lesion counts will be determined by the treatment group by analysis center interaction p-value and the skewness p-value as described in the table below:

Interaction P-Value	Skewness P-Value	Analysis Model
< 0.10	< 0.01	Ranked ANCOVA with factors of treatment, analysis center and treatment by analysis center interaction and the respective baseline lesion count as a covariate
≥ 0.10	< 0.01	Ranked ANCOVA with factors of treatment and analysis center and the respective baseline lesion count as a covariate
< 0.10	≥ 0.01	ANCOVA with factors of treatment, analysis center and treatment by analysis center interaction and the respective baseline lesion count as a covariate
≥ 0.10	≥ 0.01	ANCOVA with factors of treatment and analysis center and the respective baseline lesion count as a covariate

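### The lesion-count ANCOVA assumes one residual variance for both arms under 2:1 allocation; if the arms differ, its standard errors and intervals are miscalibrated, and naming an HC2 or arm-specific variance avoids this cheaply

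*SAP*

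**What the plan says.** For absolute change in inflammatory and non-inflammatory counts, SAP 7.9.7.1 (and Protocol 11.3) specifies an "ANCOVA with factors of treatment and analysis center and the respective baseline lesion count as a covariate". A treatment-by-center interaction is added if its p-value is below 0.10.

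The only distributional check is on the residuals: "A two-sided p-value for the skewness test significant at 0.01 will imply the use of the non-parametric method". In that case the change is ranked and the same ANCOVA is fitted. No section names a robust standard error, an arm-specific variance or an equal-variance check for the lesion counts.

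Allocation is 2:1. SAP 4.1.2 says subjects are randomized so as to "balance treatment allocation within study sites in a 2:1 fashion", and SAP 4.2 plans "a sample of 700 subjects randomized to 2 to 1 for Olumacostat Glasaretil Gel (n=467) and vehicle (n=233"). The sample size uses a single SD for each endpoint. For inflammatory change it takes "treatment means of -15.21 and -9.7 for Olumacostat Glasaretil Gel versus its vehicle", "with a standard deviation (SD) of 11.00"; for non-inflammatory change the difference is 5.03 with SD 16.72.

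Neither lesion-count sensitivity analysis in SAP 7.3.2.1 relaxes the assumption. The repeated-measures ANCOVA states no covariance structure or robust standard error, and the model-based imputation reuses the analysis model. SAP 7.3 imputes each arm separately, but the completed data then go into the single-variance model.

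**The concern.** The usual ANCOVA standard error pools the residual variance across arms. At 2:1 the pool is weighted two to one toward active, while the true variance of the treatment difference depends more on the smaller vehicle arm. At 1:1 the two weightings coincide, so the exposure comes from the allocation ratio.

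If vehicle is the more variable arm, the standard error is too small, the interval too narrow and the test too liberal. If active is the more variable arm, the reverse holds and precision is given away. Two of the three co-primary variables, and the two percent-change secondaries that use the same method, rest on this standard error. The skewness test does not look for this problem.

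**Working it through.** **1. The plan's own figures reproduce.** They use a two-sided test at alpha 0.05 with a common SD (SAP 4.2).
- Non-inflammatory, 450/225: SE = 16.72 × √(1/450 + 1/225) = 1.365; 5.03/1.365 = 3.684; power = Φ(3.684 − 1.960) = 95.8%. The plan says 95%.
- Inflammatory, 300/150: SE = 11.00 × √(1/300 + 1/150) = 1.100; 5.51/1.100 = 5.009; power = 99.9%. The plan says at least 95%.
- At 467/233 the same formula gives 96.3% for non-inflammatory and over 99.9% for inflammatory counts.

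**2. Model-based against true standard error at 467/233.** Let r be the active-to-vehicle residual variance ratio, with vehicle variance set to 1.
- Model variance = [(467r + 233)/700] × (1/467 + 1/233)
- True variance = r/467 + 1/233
- Type I error for equal means = 2 × [1 − Φ(1.96 × SE model / SE true)]

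The values of r are assumptions, because the documents give no SD by arm.
- r = 0.67: model 0.005017, true 0.005727; SE ratio √0.8761 = 0.936, so 6.4% too small. Type I error 6.7%, coverage 93.3%.
- r = 1.5: model 0.008579, true 0.007504; SE ratio √1.1433 = 1.069, so 6.9% too large. Type I error 3.6%, coverage 96.4%.
- r = 1: ratio 1, type I error 5.0%.

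Expressed as the vehicle-to-active SD ratio:

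| SD ratio | SE model / SE true | Type I error |
|---|---|---|
| 0.8 | 1.076 | 3.5% |
| 0.9 | 1.036 | 4.2% |
| 1.1 | 0.969 | 5.8% |
| 1.25 | 0.929 | 6.9% |

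**3. Simulation of the full model.** It used 700 subjects, 25 or 45 centers, and complete normal data without the interaction. The center counts are assumed; the SAP 7.5 minimum of 15 per center allows at most 46. The classical test rejected in 3.5–3.6% of trials at SD ratio 0.8 and about 7.1% at 1.25, as the closed form predicts. In the ranked model (45 centers) the distortion is smaller: 4.1% and 5.8%.

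**4. Power.** The allocation-weighted variance is held at the planned value. Inflammatory power stays above 99.9% for SD ratios 0.5 to 1.5. Non-inflammatory power, with the classical and then the correct standard error, is 97.3% and 98.1% at SD ratio 0.8, and 95.2% and 93.6% at 1.25.

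**5. Which robust estimator.** Simulated type I error in the raw model without interaction, for SD ratios 0.67 to 1.5:
- Classical: 2.6–8.5%
- HC0: 5.4–6.4%
- HC2: 5.0–5.4% (ranked model, SD ratios 0.8 to 1.5: 4.7–5.5%)
- HC3: 4.1–4.7%

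With equal variances and 45 centers, non-inflammatory power is 96.2% classical, 96.2% HC2 and 95.5% HC3.

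The interaction branch separates HC2 from HC3. Take centers at the SAP minimum of 10 active and 5 vehicle, weight them equally, and leave the baseline covariate aside. HC3 then inflates each cell's variance by n/(n − 1), so its SE is too large by √[(1.111/10 + 1.25/5)/(1/10 + 1/5)] = 1.097. Type I error becomes 2 × [1 − Φ(1.96 × 1.097)] = 3.2%. Simulation with equal variances gives 2.9%, and power falls from 95.9% to 94.0%. HC2 stays near 5%.

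**The case against.** The strongest case against acting is that ordinary ANCOVA is conventional, the documents contain no contradiction here, and nothing in them shows that the arms differ in variance. All of that stands. So does the point that for SD ratios between 0.9 and 1.1 the error is under one percentage point.

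Three stronger readings are tempting, and the documents support none of them.

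- **That Phase 2 already shows unequal variances.** Protocol 1.2 reports an LS mean change of -"10.7 for the combined vehicle QD group (P = 0.011, P = 0.014, and P = 0.011 respectively"). Dividing the differences of 3.9, 3.8 and 4.3 by the matching normal quantiles gives standard errors of about 1.53, 1.55 and 1.69, the largest for the twice-daily arm. A reader might infer a larger active variance. The P values are rounded, and neither the Phase 2 model nor the numbers analyzed are stated. If that model pooled its variance, the difference reflects sample size or missing data. This is not evidence of unequal variance.
- **That the trial's false-positive rate is 6.7%.** If the drug has no effect of any kind, both arms share one distribution and the classical test is valid. The 6.7% applies to equal means with unequal spread, on one lesion count, at an assumed ratio. The IGA logistic model has no pooled residual variance. If all three co-primaries must succeed, a marginal rate on one of them is not the trial's rate.
- **That any robust standard error will do.** HC0 is liberal with 25 to 45 center terms, and HC3 is conservative, markedly so with the interaction.

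The ranked branch softens the problem but does not remove it. What survives is that the assumption is unchecked and matters more at 2:1, and that relaxing it needs no knowledge of the variance ratio.

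**Conclusion.** The point holds as a conditional one. The lesion-count standard errors and intervals are miscalibrated if the arms' residual variances differ, and no planned lesion-count analysis would detect or correct this. At assumed active-to-vehicle variance ratios of 0.67 and 1.5, the standard error is 6.4% too small or 6.9% too large. Neither the true ratio nor its direction can be read from the documents, and there is no effect if the variances are equal.

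Inflammatory power is so high that its test conclusion would hardly change. The consequence is mainly interval coverage for both counts, and the test for non-inflammatory counts, where planned power is about 96%. These figures rest on normal, complete data; the simulations did not run the imputation step. This is an inexpensive improvement to a conventional analysis, and does not show that the planned test is invalid.

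**What to change.** Add one sentence to SAP 7.9.7.1: in each imputed data set, for both raw and ranked models and with or without the interaction, compute the treatment standard error with the HC2 heteroscedasticity-consistent estimator, or fit arm-specific residual variances, and pass that standard error to PROC MIANALYZE. Apply the same rule to the percent-change secondaries in SAP 7.9.7.2. Name the estimator, so that HC0 or HC3 is not used by default. Settle this before unblinding.

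The cost is one SAP sentence, one programming option and a slightly noisier standard error. With HC2, under 0.1 points of power are lost when the variances are in fact equal.

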7.9.7.2 Secondary Efficacy Analyses

The percent change from Baseline to Week 12 in inflammatory and non-inflammatory lesion counts will be analyzed using the same ANCOVA method described for the primary endpoint.

The proportion of subjects who are dichotomized to success (minimum 2-grade improvement from Baseline) at Week 12 will be analyzed using the same logistic analysis method described

for the primary endpoint. A stepwise process will be conducted for testing the secondary efficacy endpoints in order to control for multiplicity, refer to Section 7.6 for details.

7.9.7.3 Other Supportive Efficacy Analyses

The percent change and absolute change from Baseline to Weeks 4 and 8 inflammatory and non-inflammatory lesion counts will be analyzed using the same ANCOVA method described for the primary endpoint of absolute change in lesion counts from Baseline to Week 12. The inclusion of p-values in these efficacy analyses is to assist in characterizing the therapeutic efficacy of the active formulation and dosage regimen. No adjustments will be made for multiple comparisons for the supportive efficacy analyses.

Descriptive statistics will be presented for the following parameters by treatment group for both the ITT and PP populations:

- Frequency and percent distributions of the IGA Score at Baseline and Weeks 4, 8 and 12;
- Frequency and percent distributions of the dichotomized IGA Score at Baseline and Weeks 4, 8 and 12;
- Descriptive statistics will be used to summarize inflammatory and non-inflammatory lesion counts at Baseline and Weeks 4, 8 and 12;
- Descriptive statistics will be used to summarize the absolute and percent change in inflammatory and non-inflammatory lesion counts at Weeks 4, 8 and 12;
- Descriptive statistics will be used to summarize the Acne Patient Self-Questionnaire assessments at Weeks 4, 8 and 12. Satifasction questions answered at Week 12 will be summarized with frequency and percent distributions.

7.9.8 Safety Analyses

7.9.8.1 Extent of Exposure

The extent of exposure to study drug in each treatment group will be summarized by amount of study drug used (computed from study drug tube weights) and anatomical areas treated. Facial exposure will be summarized by total number of days of exposure, total number of applications, number of missed applications and number and percentage of subjects who are compliant. A subject will be considered compliant with the dosing regimen if the subject applied 80% to 120% of the expected number of applications while enrolled in the study. Total number of days of exposure will be computed as follows:

Total Exposure = Date of Last Application – Date of First Application + 1.

Dosing deviations reported for areas other than the face will not be considered in compliance calculations. On the date of first application and the date of last application, some subjects were

to apply one dose and others were to apply two doses, depending on the time of the study visit. After the date of first application and before the date of last application subjects were expected to apply two doses. Missed applications will be calculated from dosing deviations which report zero or one application on a given date. Extra doses will be calculated from dosing deviations which report more than the expected number of applications on a given date. The total number of applications will be calculated as follows:

If the Date of First Application is not equal to Date of Last Application, then

Total Applications = 2*(Date of Last Application – Date of First Application – 1)

- + Expected Applications on Date of First Application
- + Expected Applications on Date of Last Application
- Missed Applications + Extra Applications.

If the Date of First Application = Date of Last Application, then

Total Applications = Expected Applications on Date of First Application

- Missed Applications + Extra Applications.

Treatment compliance will be based on the expected number of doses given the treatment period duration. Treatment period duration will be computed from the Baseline/Day 1 visit date and the Week 12/Early Termination (ET) visit date. If a subject does not have a Week 12/ET visit, treatment period duration will be calculated based on the date of last dose or last completed visit date, whichever is later. That is, treatment period duration will be computed from the Baseline/Day 1 date and the end of treatment period date, where the end of treatment period date is given by

- If the subject completed the Week 12/ET visit, the end of treatment period date will be:
 - The date of the Week 12/ET visit if the expected number of applications on the date of last application is one;
 - The day prior to the Week 12/ET visit if the expected number of applications on the date of last application is two;
- If the subject did not complete the Week 12/ET visit, the end of treatment period date will be the date of last dose or last completed visit, whichever is later.

Then treatment period duration may be calculated as:

Treatment Period Duration = End of Treatment Period Date – Day 1 Date + 1.

If the treatment period duration exceeds 88 days, treatment period duration will be considered 88 days. In addition to treatment period duration, missed applications due to treatment-related AEs

will be considered when determining the expected number of doses for each subject. If a treatment-related AE (regardless of location) requires interruption of study drug during the treatment period, missed applications during the AE (onset date to resolution date) will be deducted from the expected number of doses. Therefore, the expected number of applications will be calculated as:

Expected Applications = 2*(Treatment Period Duration - 2)

- + Expected Applications on Date of First Application
- + Expected Applications on Date of Last Application
- Applications Missed Due to a Treatment-Related AE.

If Treatment Period Duration = 1, then

Expected Applications Expected Applications on Date of First Application

– Applications Missed Due to a Treatment-Related AE.

Percent compliance will be calculated from total number of applications and total number of expected applications as follows:

Percent Compliance = 100*(Total Applications/Expected Applications).

Percent compliance will not be calculated for subjects who are lost to follow-up.

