8 STUDY PROCEDURES

The procedures required for subject evaluation at each study visit are outlined below and in the study Schedule of Visits and Procedures (see Appendix 1). The timing of each study day is relative to the day of initial dosing (Baseline/Day 1). Visit windows are provided to allow study sites some flexibility in maintaining the study visit schedule for participating subjects. Out of window visits may be unavoidable in certain circumstances. Out of window visits are not considered deviations to the protocol.

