9.4.8 Dosing Changes due to AEs

Dose interruptions are allowed should a subject experience intolerable treatment-related adverse events (e.g., pruritis) on study. In cases where the Investigator feels a dose interruption is warranted, the subject should be instructed to interrupt study drug application to allow symptoms to resolve. Subjects should be instructed to return to the twice daily application regimen within 2 days of dose interruption.

Dosing interruptions are to be recorded in the subject diary as a missed dose.

Study drug must be discontinued if an adverse event is deemed persistent and if continuation of study drug would not be in the best interest of the subject.

Refer to Section 10.3 for further information regarding discontinuation of study drug or early withdrawal

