7.9 Statistical Analysis

All analyses will be performed by QST. All summary tables and data listings will be prepared utilizing SAS® software. The standard operating procedures of QST will be followed in the creation and quality control of all data displays and analyses.

All data collected at scheduled time points will be summarized, regardless of treatment with study drug. Post-treatment assessments for subjects who discontinue treatment but continued to be followed in the study will be included in summaries.

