7.9.2 Visit Windowing

Data will be summarized based on nominal visit indications with the exception of data captured at early termination and unscheduled visits. Data from early termination and unscheduled visits will be summarized based on mapped visit values. The analysis windows for early termination and unscheduled visits are presented in the following table.

Scheduled Visit	Target Study Day	Window (Days)
Week 1	8	5 to 18
Week 4	29	19 to 42
Week 8	57	43 to 70
Week 12	85	71 to 98

Analysis Windows for Efficacy and Safety Assessments

Data collected at early termination and unscheduled visits prior to study day 5 will not be analyzed, with the exception of those identified as baseline values. Data collected at early termination and unscheduled visits after study day 98 will not be included in analyses.

The definition for the study day included in each study window is defined as below:

Study Day Prior to Day 1 = Visit Date – Day 1 Date

Study Day On or After Day 1 = Visit Date - Day 1 Date + 1.

If an assessment's mapped visit is a visit at which the subject has data from a scheduled visit present, or if no analyses are planned for the assessment at the mapped visit, the data collected at the early termination or unscheduled visit will not be included in analyses.

In the event of multiple values from unscheduled or early termination assessments within an analysis window, the value closest to the scheduled visit target study day will be used for analyses. If two values tie as closest to the time point (for example, one value is before and the other value is after the time point), then the later value will be selected.

Data collected at all visits will be included in the data listings with visit presented as reported by the site.

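### Percent compliance in SAP 7.9.8.1 can compare doses over different days: the 88-day cap limits expected doses only, and missed doses have no end date

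*SAP*

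**What the plan says.** SAP 7.9.8.1 builds percent compliance from two counts.

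- **Total applications** span the first to the last application: "Total Applications = 2*(Date of Last Application – Date of First Application – 1"), plus the doses expected on those two dates, minus missed and plus extra applications. No cap is applied. On missed doses the SAP says: "Missed applications will be calculated from dosing deviations which report zero or one application on a given date". The sentence before it reads: "After the date of first application and before the date of last application subjects were expected to apply two doses".
- **Expected applications** run from Day 1 to the end of the treatment period. For a subject with a Week 12 or early termination visit, that end is the visit date if one dose is expected on the last application date, and the day before the visit if two are. Here a cap applies: "If the treatment period duration exceeds 88 days, treatment period duration will be considered 88 days". Doses missed because of a treatment-related AE are deducted.

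The 80–120% band is one of the PP exclusions in SAP 7.8.4, beside an exclusion for Week 12 visits out of window by ± 5 days. The same section keeps in PP those who stop for a related AE or documented lack of effect. Efficacy analyses are presented for both ITT and PP.

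Late visits are foreseeable. Protocol section 8 states: "Out of window visits are not considered deviations to the protocol". SAP 7.9.2 adds: "Data will be summarized based on nominal visit indications", with early termination and unscheduled visits as the exception, so a late scheduled Week 12 visit still counts as Week 12.

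**The concern.** A compliance ratio is interpretable only if doses taken and doses due are counted over the same days. Here they can differ in two ways.

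1. Past Day 88 the denominator stops and the numerator continues, so late doses can make up for earlier misses and the score is too high.
2. The numerator covers dates up to the last application, but the missed doses subtracted from it carry no date limit. A missed day after the last application, if recorded, lowers the score once because the numerator stops early and again because the miss is subtracted.

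At stake are classification at the 80% limit, and with it membership of the PP set, and the descriptive table of compliance, total applications and missed applications.

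**Working it through.** The documents report no compliance result to reproduce, so the formulas were applied as written. Let T be the treatment period duration, L the study day of last application, and e1 and eL the doses expected on the first and last application dates.

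- Expected = 2 × (min(T, 88) − 2) + e1 + eL − doses missed for a related AE
- Total = 2 × (L − 1 − 1) + e1 + eL − missed + extra

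**Baseline check.** Week 12 on Day 85 (SAP 7.9.2), one dose on each end date, full dosing: total = 2 × 83 + 2 = 168 and expected = 2 × 83 + 2 = 168, or 100%. The terms agree when dosing runs to the end of the period and the cap is not reached.

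**Cap.** With e1 = eL = 1, expected stops at 2 × 86 + 2 = 174. The fewest whole doses that reach 80% is 140 (0.80 × 174 = 139.2).

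| Last application and visit | Doses due without cap | Full dosing scores | True share at 140 doses |
|---|---|---|---|
| Day 89 | 176 | 176/174 = 101.1% | 140/176 = 79.5% |
| Day 90 | 178 | 178/174 = 102.3% | 140/178 = 78.7% |
| Day 94 | 186 | 186/174 = 106.9% | 140/186 = 75.3% |
| Day 106 | 210 | 210/174 = 120.7% | 140/210 = 66.7% |

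With two doses on the first day the cap is 175 and the pass mark is again 140 doses: 140/179 = 78.2% at Day 90 and 140/187 = 74.9% at Day 94.

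The visit window is Day 85 ± 4 (protocol 8.7), so Day 89 is in window. If one dose is due that day, the period ends on the visit date and T = 89, one day over the cap. If two are due, the period ends the day before, T = 88, and the cap does not bite.

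**Reach into PP.** The ± 5 days exclusion can mean Day 85 ± 5, so Day 90 at the latest, or five days beyond the ± 4 window, so about Day 94. The cap can therefore admit to PP subjects whose true share is about 78% to under 80% on the first reading, or about 75% to under 80% on the second. Later rows affect only the compliance table.

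**Missed doses after the last application.** Take Week 12 on Day 85, e1 = 1 and eL = 2, so the period ends on Day 84 and expected = 2 × 82 + 3 = 167. Suppose no doses are taken on the last k days, there are no other misses, and those days are recorded as zero-dose deviations.

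- True: (167 − 2k)/167
- By formula: (167 − 4k)/167

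| k | True | By formula |
|---|---|---|
| 8 | 151/167 = 90.4% | 135/167 = 80.8% |
| 9 | 149/167 = 89.2% | 131/167 = 78.4% |
| 10 | 147/167 = 88.0% | 127/167 = 76.0% |
| 16 | 135/167 = 80.8% | 103/167 = 61.7% |
| 17 | 133/167 = 79.6% | 99/167 = 59.3% |

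So k = 9 to 16 is misclassified. With two doses on both end dates (168 expected) the range is again 9 to 16; with 5% other misses it is 7 to 13, and with 10% it is 5 to 9. If days after the last application are not recorded as deviations, only the 'True' column arises and early stopping is penalised once, as it should be.

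**The case against.** The strongest objection concerns the missed doses. The sentence preceding the rule on missed applications sets the two-dose expectation only between the first and last application dates. On that reading a day after the last application has no expected dose and cannot be a deviation, so nothing is subtracted twice. The protocol text that might suggest otherwise is weak. Section 9.4.8 says "Dosing interruptions are to be recorded in the subject diary as a missed dose", but it concerns interruptions with a return to dosing within 2 days, so those misses fall before the last application. Section 6.6 has any missed applications recorded in the eCRF without saying that recording continues after last use. SAP 7.9 says "Post-treatment assessments for subjects who discontinue treatment but continued to be followed in the study will be included in summaries", which concerns assessments, not dosing records. A reader might infer that the SAP certainly double-counts and so removes early stoppers from PP. The documents do not support that. They also do not exclude it: the rule has no end date, and the deduction for related AEs runs over a treatment period that can extend past the last application. The ambiguity stands; the certainty does not.

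On the cap, it is fair to say that treatment is planned for 12 weeks, that kits are supplied for 12 weeks, and that limiting expected doses near that length is a legitimate choice. The SAP gives no reason for 88. But a deliberate limit on doses due should also limit the doses counted against them.

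A reader might also infer from the 120.7% figure that a fully dosed subject could fail PP on compliance. That needs a last application at about Day 106, which the Week 12 exclusion removes on either reading.

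Finally, a denominator that runs past the last application is not a fault in itself; it is how early stopping lowers compliance.

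**Conclusion.** The concern holds in a limited form, and its severity is minor. The cap mismatch follows directly from the formulas. In PP it can pass subjects up to about 2 percentage points below the 80% limit (Day 90) or about 5 points below it (Day 94), and an in-window Day 89 visit with one dose due already exceeds the cap.

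The double penalty is conditional on zero-dose days after the last application being logged as deviations. Even then, the PP error is confined to subjects who stop for reasons other than a related AE or documented lack of effect, about 9 to 16 days before the end of the period if they have no other misses, and who still attend Week 12.

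The number of subjects affected cannot be computed from the documents. The ITT analyses, including the ordered secondary tests that SAP 7.6 restricts to ITT, do not depend on compliance.

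**What to change.** Amend SAP 7.9.8.1 before unblinding:

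1. Use the same end date for both terms. Either drop the 88-day cap, or count total applications only through the capped end date, taking the last-day dose count at that same date in both terms. If a cap is kept, make it agree with the Day 89 limit of the Week 12 window.
2. In total applications, subtract only missed applications dated from the first through the last application.

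Optionally, report the number of missed applications separately over the whole treatment period. Otherwise a subject who stops 10 full days early, at two doses a day, shows 0 missed where 20 were not taken. Early stopping would still be visible in days of exposure, total applications and percent compliance, so this is a matter of presentation.

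The cost is two sentences of wording and a small programming change, with no new data.
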